## 4. Design and Procedures

This is a single-center, randomized, blinded PK study of ambrisentan in children ages  $\geq 24$  months and  $\leq 120$  months with single ventricle anatomy. There will be up to 20 subjects enrolled; 16 will receive ambrisentan and 4 will receive placebo. A small placebo control group is warranted to ensure that any treatment effect is not a result of post-operative improvement. Patients will be enrolled at the time of their routinely scheduled Fontan surgery.

**Initial Dose:** Oral ambrisentan 2.5 – 5 mg, single dose, once daily (nasogastric and gastrostomy tube administration will be considered only when a nasogastric or gastrostomy tube is already in place as part of routine post-operative care). Subjects will be randomized by Investigational Drug Services (IDS) to placebo (n=4) or oral ambrisentan (n=16) using permuted blocks. Subjects will receive either an oral suspension (2.5 or 5mg) or a 5mg tablet depending on their ability to swallow a tablet. To begin to ensure safety, the initial 5 subjects enrolled in the study (at least 4 active drug) will receive a dose of 2.5mg in a liquid suspension prepared by IDS. After enrollment of these subjects we will perform a preliminary PK/safety analysis and evaluate ambrisentan exposure. If the drug is well tolerated (no grade III or greater adverse events) and exposure is less than the target exposure of 500-800ng/mL, then we may increase the dose to 5mg/dL provided via tablet in those able to take a tablet or suspension for all others. If drug exposure is less than 100ng/mL then we will enroll additional study subjects to ensure that at least 16 study subjects achieve adequate drug exposure. If drug exposure is in the target range then we will continue to enroll study subjects to receive the 2.5mg suspension.

As summarized below, study drug will be discontinued for any grade 3 or greater adverse event. If this occurs then IDS will be permitted to unblind the study patient to allow for appropriate adverse event reporting. Drug administration will start on post-operative day #1 with initiation of oral feeds. Study drug/placebo will be prepared and delivered to the patient bedside by investigational drug services and administered orally. Subjects will continue on study drug for 3 days.

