## 5. Study medication

### Rationale for Dose Selection

Preliminary data from 16 children with pulmonary hypertension using once-daily doses of 5 mg demonstrate similar  $C_{max}$  and  $AUC_{24hr}$  to those seen in adult patients. This PK study included children and adolescents ages 2 years – 18 years including 9 subjects age  $\leq 10$  years. Weight ranged from 13kg to 52 kg. The half-life of elimination was 7.6 hours (range 5.4–15.3 hours), and there was improvement in hemodynamic parameters (mean pulmonary arterial pressure  $55\pm 18$  mm Hg decreased to  $45\pm 20$  mm Hg after initiation of ambrisentan,  $p=0.04$ ). Ambrisentan was well tolerated in all patients with no serious adverse events. In post-operative Fontan patients, I anticipate decreased bioavailability due to post-operative bowel wall edema but also decreased hepatic elimination. I will perform a preliminary PK/PD analysis after enrolling the first 5 subjects (at least 4 active drug) and adjust the dosing to achieve target peak concentrations of 500–800 ng/mL, a range that has demonstrated therapeutic efficacy as well as safety in adults. To maintain blinding, we will request that ambrisentan levels be sent from the commercial

laboratory directly to IDS. IDS will remove study patient identifiers and then forward the drug levels for PK analysis and determination of dose adjustment.

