## **13. Data Analysis & Statistical Considerations:**

There will be up to 50 subjects enrolled and receiving drug in this study. Additional subjects will be enrolled to ensure that at least 20 subjects have at least 4 evaluable PK samples and that at least 16 subjects have ambrisentan peak exposure > 100ng/dL. Subjects who have only 1 evaluable sample will be included in the analysis. Descriptive statistics such as number of observations, mean, median, 95% confidence interval, standard deviation, standard error, minimum, and maximum will be presented for continuous variables (such as age, weight, etc.). Other descriptive statistics such as counts, proportions, and/or percentages will be presented to summarize discrete variables (such as race, sex, etc.). Pharmacokinetic parameters will be calculated using non-compartmental analysis using WinNonlin software (Pharsight Corporation, Mountain View, CA). As previously mentioned, there will be an interim PK analysis that may alter the dosage.

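### Enrolment can run past 20 on targets that depend on ambrisentan children, but allocation is given only as 16 active and 4 placebo, with no rule for allocating or blinding the added children

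*Combined protocol and SAP*

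**What the plan says.** All references are to the combined protocol and SAP.

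- **Planned size (Section 4).** "There will be up to 20 subjects enrolled; 16 will receive ambrisentan and 4 will receive placebo".
- **Allocation (Section 4).** "Subjects will be randomized by Investigational Drug Services (IDS) to placebo (n=4) or oral ambrisentan (n=16) using permuted blocks". The block size is not given. The only placebo number anywhere in the plan is 4.
- **First cohort (Section 4).** "the initial 5 subjects enrolled in the study (at least 4 active drug) will receive a dose of 2.5mg".
- **Exposure top-up (Section 4).** If exposure is below 100 ng/mL, "we will enroll additional study subjects to ensure that at least 16 study subjects achieve adequate drug exposure".
- **Top-up targets (Section 13).** "Additional subjects will be enrolled to ensure that at least 20 subjects have at least 4 evaluable PK samples", and also that "at least 16 subjects have ambrisentan peak exposure > 100ng/dL". The first is a count of samples and the second is a drug level.
- **Ceiling.** The Synopsis and Section 4 give up to 20 enrolled. Section 7 gives 50 consented for up to 20 evaluable. Section 13 gives up to 50 enrolled and dosed.
- **Handling of levels (Section 5, Rationale for Dose Selection).** The laboratory sends levels to IDS, which removes identifiers before forwarding them. The same section expects lower absorption after surgery: "I anticipate decreased bioavailability due to post-operative bowel wall edema".

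The plan does not say whether the blocks continue past 20, whether added children stay blinded, or whether placebo children count toward the 20 with usable PK samples.

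**The concern.** Section 4 justifies the placebo group as the guard against mistaking ordinary recovery after surgery for a drug effect. That guard works only if placebo children are enrolled over the same period and staff cannot tell the arms apart.

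The exposure target can be met only by children on ambrisentan. If the placebo count is held at 4 while enrolment continues toward that target, every child after the 16 + 4 list is used up is on ambrisentan. Staff need no drug level to work this out, because position in the enrolment sequence is enough. Routing levels through IDS therefore does not prevent it.

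What is exposed is the judgement-based part of the study: chest tube duration and hospital stay (secondary outcomes in Section 2), and the decision in Section 14 on whether an adverse event is related to study drug. Separately, a target of 20 children with usable PK data sits awkwardly beside an active arm of 16.

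**Working it through.** **1. The plan's own split.** At 4:1, 20 × 4/5 = 16 and 20 × 1/5 = 4, so the stated figures reproduce. A block of five (4 active, 1 placebo) would also guarantee at least 4 active among the first 5. Blocks of 10 or 20 would do so with probability only 0.78 or 0.75. A block of five is a plausible inference, but the plan does not state it.

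**2. How readily the exposure target calls for more children.** Exactly 16 active are planned and 16 must qualify, so a single shortfall means a top-up. Let q be the chance that one ambrisentan child passes the cut-off. The documents give no value, so q is assumed throughout. The chance that all 16 pass is q^16, and the expected number of active children required is 16/q.

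| q (assumed) | q^16 | 16/q | rounded up | beyond 16 |
|---|---|---|---|---|
| 1.00 | 1.00 | 16.0 | 16 | 0 |
| 0.95 | 0.44 | 16.8 | 17 | 1 |
| 0.90 | 0.19 | 17.8 | 18 | 2 |
| 0.80 | 0.03 | 20.0 | 20 | 4 |
| 0.70 | 0.003 | 22.9 | 23 | 7 |

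**3. The target of 20 with usable PK samples.**
- *Ambrisentan children only:* 20 − 16 = 4 more active are needed even with no failures. The total is 20 + 4 = 24 if placebo stays at 4, or 20/0.8 = 25 (20 + 5) at 4:1.
- *All sampled children:* 16 + 4 = 20, so the target is met without a top-up only if every planned child gives four usable samples. With a per-child success probability of 0.95, 0.90 or 0.80 (assumed), q^20 is 0.36, 0.12 or 0.01. Up to 4 of the 20 would then carry no ambrisentan PK.

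**4. Effect on the comparison.** With placebo held at 4, its share falls from 4/20 = 20% to 4/24 = 17%, and to 4/50 = 8% at a ceiling of 50. For a difference in means with equal variances, the standard error is proportional to √(1/active + 1/placebo):

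| active + placebo | total | factor |
|---|---|---|
| 16 + 4 | 20 | 0.559 |
| 20 + 4 | 24 | 0.548 |
| 20 + 5 | 25 | 0.500 |
| 46 + 4 | 50 | 0.521 |
| 40 + 10 | 50 | 0.354 |

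With 4 placebo children the factor cannot fall below √(1/4) = 0.500, however many active children are added. At 25 children the 4:1 design already reaches that value.

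**5. Units.** 100 ng/dL is 1 ng/mL, so the cut-offs in Sections 4 and 13 differ 100-fold. The frequency of top-up depends on which applies.

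**The case against.** The strongest reply is that no section closes the schedule at 4 placebo. The counts belong to the 20-child plan, and continuing 4:1 blocks is compatible with the text and would keep concurrent, blinded placebo. This stands. A reader might infer that every child beyond 20 *is* known to be on ambrisentan; the documents support only that this *would* follow if the count of 4 is kept, and that nothing prevents it.

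Second, the figures 20 and 16 in Section 13 match the planned total and the active arm, and Section 10 writes PK sampling per patient, without limiting it to the active arm. The 20 may therefore mean all sampled children. In that case a placebo child with too few samples could also prompt a top-up, and position in the sequence would be less revealing. So the 20 target is not strictly impossible with 16 active. That reading has its own cost, shown in step 3.

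Third, the Section 4 trigger follows the analysis of the first 5 children and can be read as a single cohort decision. Section 13, however, states the requirement as a count of children, which supports a running tally.

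Fourth, failure may be rare. The Section 13 cut-off as printed is very low, and even 100 ng/mL is well below the plan's 500–800 ng/mL target range. This too stands, and it is why the table includes q = 1.

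Finally, one might infer that the active arm will be reported as a selected group of good absorbers. The plan defines no such analysis set. Section 13 keeps children with a single usable sample, and Section 14 summarises hemodynamics without an exposure filter. The bias would arise only if outcomes were summarised by achieved exposure.

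**Conclusion.** The concern holds as a conflict between fixed allocation counts and open-ended enrolment targets, with the governing rule missing. Followed literally, the plan yields added children whose treatment can be deduced and who have no concurrent placebo, which defeats the stated reason for having placebo.

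The size depends on the reading. If the 20 refers to ambrisentan PK, at least 4 children beyond the 16 are certain to be needed. If only the exposure target causes top-up, the expected number runs from none at q = 1 to about 7 at q = 0.70; these rates are illustrative and have no source in the documents.

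The consequence is moderate. This is a descriptive Phase I/II pilot with no hypothesis test or power claim, and the estimation of ambrisentan PK parameters does not itself rely on placebo. The damage falls on the placebo-controlled hemodynamic and recovery comparisons and on adverse event attribution. It should be corrected before enrolment passes 20.

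**What to change.** 1. In Section 4, replace the fixed placebo count with a 4:1 ratio, and state that IDS continues the permuted blocks for every child added beyond 20, under the same blinding.
2. In Section 13, state the PK-sample target for ambrisentan children only and make it consistent with 16. If 20 ambrisentan children are really wanted, plan for 20 + 5 = 25 from the start.
3. Have IDS or an unblinded pharmacologist judge when the targets are met and tell the study team only whether to continue or stop enrolling. IDS already randomizes and receives the levels, so this adds little.
4. Say that all dosed children stay in the hemodynamic, clinical and safety summaries by assigned arm, with the exposure cut-off used only for PK summaries.
5. Reconcile the maximum enrolment (20 enrolled, 50 consented, or 50 dosed) and the cut-off unit (ng/mL in Section 4, ng/dL in Section 13), and say whether the Section 4 trigger is a single decision or a running count.

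The cost is protocol wording, a longer list at IDS, and about one extra placebo child for every four active children added. Whether that fits under the ceiling depends on how item 5 is settled.

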### **Study Procedures**

1. Record the start and stop time of ambrisentan administration and all concomitant drugs.
2. Hemodynamic evaluation performed during pre-operative cardiac catheterization (obtained as part of usual clinical care), prior to initiation of study drug, and at 0-1,1-6,18-30 and 40-60hrs after administration of the first ambrisentan dose (blood samples will be collected only if central monitoring lines remain or if they can be timed with a routine lab collection)

- a. Record Fontan, common atrial, and systemic arterial pressures from existing central lines that are placed as part of routine post-operative care.
- b. Collect study labs (coincident with scheduled PK levels – see below):
  - i. plasma samples for biomarkers (endothelin 1 [ET1], brain natriuretic peptide [BNP]).
- c. Record oxygen saturation from routinely collected arterial and venous blood gases.
- 3. PK blood samples (500 µL, up to 7 per patient) and pressure measurements will be obtained at baseline and at 1–2, 3–4, 5–6, 8–12, 12–16, 24, and 48 hours post-initial drug administration.
- 4. Adverse events will be collected during and for 1 month after the last study drug administration. Results will be tabulated by organ system.
- 5. Physical examination will be performed within 24 hours after administration of study drug and once daily during study enrollment.
- 6. Record all AEs and SAEs.
- 7. Record all concomitant medication administered 24 hours after administration of study drug.
- 8. Up to 4 scavenge samples will be obtained from the clinical laboratory from samples collected in the 24 hours following ambrisentan administration. Scavenged samples are left over heparinized plasma samples from these children that are collected from the clinical laboratory prior to discarding.

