### **PK Sampling**

A limited PK sampling scheme will be employed such that no more than 3000 µl of blood is obtained.

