## **12. Risk/Benefit assessment:**

Blood volume: In order to minimize the amount of blood sampling, hematology and chemistry laboratory measures will be obtained per local standard of care; and a limited PK sampling scheme will be employed such that no more than a total of 3000  $\mu$ l of blood is obtained from each patient for PK analysis. Blood samples will be collected in 500  $\mu$ L aliquots. In addition a total of 4 samples will be obtained for biomarker assessment. Blood samples will again be collected in 500  $\mu$ L aliquots. No more than 2000  $\mu$ l will be collected for biomarker assessment. During the study samples will be obtained from indwelling central venous catheters. If central venous lines are not available then samples will be obtained from a peripheral IV if present. If no IV is present then every effort will be made to time the PK sampling with line draws or heel sticks for normal laboratory monitoring including chemistries, blood gases, and accucheks. This should result in 1 or 2 additional line draw or possibly heel sticks specifically for PK sampling in any given child.

Drug related adverse effects:

Below is a summary of adverse events associated with ambrisentan use from the pivotal trials as reported on the drug label:

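### Seven permitted PK draws of 500 µL exceed the plan's own 3000 µL cap, the exposure threshold behind the count of 16 is stated in units 100-fold apart, and one-sample subjects enter a non-compartmental analysis with no rule on what they contribute

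*Combined protocol and SAP*

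**What the plan says.** **Blood volume.** Section 10 (Study Procedures, item 3) sets PK samples of 500 µL, "up to 7 per patient) and pressure measurements will be obtained at baseline and at" seven later times, the last at 48 h. Section 10 (PK Sampling) says "A limited PK sampling scheme will be employed such that no more than 3000" µL is taken. Section 12 (Risk/Benefit assessment) repeats the limit per patient, "a limited PK sampling scheme will be employed such that no more than a total of 3000" µL, and repeats the 500 µL aliquot. Biomarker blood is additional, with its own 2000 µL limit. Item 8 of Study Procedures adds leftover clinical plasma: "Up to 4 scavenge samples will be obtained from the clinical laboratory".

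**Threshold.** Section 4: "If drug exposure is less than 100ng/mL then we will enroll additional study subjects", so that at least 16 are adequately exposed. Section 13 enrolls further subjects so that "at least 16 subjects have ambrisentan peak exposure > 100ng/dL". The target peak in Section 5 is 500–800 ng/mL.

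**Sparse subjects.** Section 13 enrolls until "at least 20 subjects have at least 4 evaluable PK samples", then states "Subjects who have only 1 evaluable sample will be included in the analysis". The synopsis and Section 13 name non-compartmental analysis in WinNonlin and no other PK method.

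**The concern.** PK is part of the primary objective, and each of these items is a working rule for it.

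- The volume cap is a per-patient limit given in the risk section. Staff who follow the sampling schedule to its permitted maximum would break it.
- The count of 16 decides whether more children are enrolled. Two people applying Sections 4 and 13 could reach different answers from the same data.
- One concentration cannot support the parameters that non-compartmental analysis is meant to deliver. The plan does not say which summaries a one-sample subject joins, whether that subject can count toward the 16, or how the level is used in the assessment after the first five subjects. If a late level were taken as a peak, exposure would look lower than it was.

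**Working it through.** **1. Blood volume.** Inputs: 500 µL per draw and up to 7 draws (Section 10, item 3); cap 3000 µL (Section 10, PK Sampling; Section 12).

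- The cap is reproduced by 3000 / 500 = 6 draws.
- The permitted maximum is 7 × 500 = 3500 µL. The excess is 3500 − 3000 = 500 µL, and 500 / 3000 = 17%.
- Biomarker blood (4 × 500 = 2000 µL) has a separate allowance and does not enter. Scavenge samples are leftover plasma, so they add no draw. Nothing says that they replace one.
- Eight times are listed (baseline plus seven). If baseline is a pressure reading only, seven draws remain, so the gap stays.

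**2. Threshold.** 1 dL = 100 mL, so 100 ng/dL = 1 ng/mL and the ratio to 100 ng/mL is 100. Against the lower target bound of 500 ng/mL, the Section 13 figure is 1/500 = 0.2% of target, and the Section 4 figure is 100/500 = 20%. As written in Section 13, the rule would screen out almost nobody who absorbed the drug.

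**3. A lone sample as a share of the true peak.** Input from Section 5: half-life 7.6 h (range 5.4–15.3 h). Assumptions, not in the documents: one-compartment oral model, first dose only, absorption rate ka 0.5, 1 or 2 per h, samples at window midpoints.

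Share = [exp(−kt) − exp(−ka·t)] / [exp(−k·tmax) − exp(−ka·tmax)], with k = ln 2 / half-life and tmax = ln(ka/k) / (ka − k).

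Example, half-life 7.6 h and ka = 1: k = 0.0912, tmax = 2.63 h, and the share at 24 h = 0.112 / 0.715 = 0.157.

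| Sample time | Share, half-life 7.6 h | Share, half-life 5.4–15.3 h | True peak at which the sample reads 100 ng/mL (7.6 h) |
|---|---|---|---|
| 10 h | 0.488–0.706 | 0.36–0.88 | 142–205 ng/mL |
| 14 h | 0.339–0.497 | 0.21–0.74 | 201–295 ng/mL |
| 24 h | 0.136–0.200 | 0.06–0.47 | 499–735 ng/mL |

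The last column is 100 / share. With the threshold at 100 ng/mL, a lone 24 h sample can fall below it although the true peak was in the target range. At 1 ng/mL the last column is divided by 100 (5.0–7.4 ng/mL at 24 h), and such misclassification is negligible.

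**4. If a lone level were averaged in as a peak at the interim.** Assume four active subjects with equal true peaks, one of them with a lone sample of share f. The mean is (3 + f)/4 of the truth.

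- 10 h: 0.872–0.927, which is 7–13% low.
- 24 h: 0.784–0.800, which is 20–22% low.
- Dividing 500 ng/mL by these ratios, the mean would read below the lower target bound only for true peaks between 500 and about 540–573 (10 h) or 625–638 (24 h) ng/mL.

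**The case against.** **Volume.** Seven is a maximum, and the cap can be read as governing how many draws are made. A child with six draws complies. That stands, and the excess arises only with full sampling. It does not reconcile a permitted maximum with a lower limit. A reader might go further and infer eight draws (4000 µL) from the eight listed times. The text does not support that, because it stops at seven and baseline may be a pressure reading only.

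**Sparse subjects.** The analysis that admits them is not defined. A reader might infer that their levels are used as peaks in the dose assessment, or that half-lives would be reported for them. The plan says neither, and no slope can be fitted to one point. What remains is a missing rule. Lone late samples may also be rare: Section 12 places the first dose in the ICU with central lines as the first sampling source, and scavenge samples may help, although the plan does not say whether they count as evaluable. The dose increase in Section 4 is discretionary.

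**Minimum sample number for the count.** It is tempting to require four samples for the count of 16 as well. That would be wrong. The rule is one-sided, so a single level above the threshold already proves that the peak exceeded it. A minimum number would discard valid subjects and could enroll extra children.

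**The 48 h sample.** Under once-daily dosing it follows the second dose, and a reader might infer that it would distort a first-dose terminal slope. The plan never assigns it that role, and Section 10 sets a 40–60 h hemodynamic and biomarker window with which it coincides. It is not part of this point.

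**Conclusion.** Two conflicts hold on the text alone and need no model: 3500 µL permitted against a 3000 µL limit (17% over when all seven draws are made), and a threshold for further enrollment that differs 100-fold between Sections 4 and 13. The documents must be reconciled; this review does not say which figure is right.

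The third part is smaller. One-sample subjects are admitted to a PK analysis whose only named method cannot give them a half-life or a usable AUC, and no rule states what they contribute. Any peak read from a late sample is biased downward. After the peak the direction does not depend on the assumed absorption rate; the size does. Frequency is unknown, so no overall bias in the trial's PK results can be claimed. The consequence for the count of 16 matters only if 100 ng/mL is the intended threshold.

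**What to change.** 1. Reconcile the number of PK draws, the aliquot volume and the 3000 µL cap in Section 10 (Study Procedures and PK Sampling) and Section 12, so that the permitted maximum meets the stated limit. Say whether baseline includes a PK draw.
2. Reconcile the threshold units in Sections 4 and 13.
3. Limit half-life and AUC summaries to subjects whose samples support them, for example the plan's own four evaluable samples, with an estimable terminal slope for half-life and extrapolated AUC. Give the number of subjects behind each summary, and report sparser subjects as concentrations by actual time since dose. State whether scavenge samples count as evaluable.
4. For the count of 16, count any subject with an observed level above the reconciled threshold, whatever the number of samples. Treat a subject with only late samples below it as not assessable, not as inadequately exposed.
5. At the interim, show sparse subjects' levels with their sampling times as lower bounds on the peak. Do not average them in as peaks.

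The cost is wording in Sections 4, 10, 12 and 13. A few sparse subjects leave the parameter tables but stay in the concentration listing. A subject who is not assessable does not count toward the 16, as would already be so if the late level were read as the peak.
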